#### ANALYSIS PLAN

Data will be entered into a secure Microsoft Access database. Entry to the database is limited to key personnel and is password protected at the point of the workstation and the application. Standard double-entry and data checking approaches will be performed for all measures.

General Analytic Approach: Descriptive statistics will be performed on all study variables. In order to mitigate potential bias due to transient improvements in either sleep or BP dipping, we will utilize a 6-wk run-in phase after which participants will have their sleep efficiency and BP dipping markers re-assessed to ensure stability. Although we do not anticipate significant variation in either sleep or BP parameters during this pre-treatment phase, we will exclude participants who no longer meet inclusion criteria following the 6-wk run-in period. This practice has been shown to result in an increased magnitude of treatment improvements and therefore may improve the statistical power and potential precision of the proposed analyses. Markers of sleep efficiency and BP dipping collected after our run-in phase will therefore be used as our baseline assessment measures.

Regression-based analytic approaches will be used to examine associations between improved sleep efficiency, ABP indices, and mechanisms of CVD risk. In order to minimize potential confounding of treatment improvements due to either misdiagnosis or transient fluctuations in sleep, we will use assessments collected after the run-in period as our baseline time point. For our 6-week outcomes, improvements in sleep efficiency and ABP will be examined using simple regression analyses as detailed below. In contrast, our 6-month outcomes will be examined using repeated measures mixed models with an unstructured covariance matrix, using both 6-week and 6-month levels of the outcome modeled jointly. Incorporating both outcomes into a unified, mixed modeling approach will allow us to examine improvements in sleep as they associate with trajectories of BP dipping improvements and also allows for more robust handling of missing data.

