Power and Sample Size Considerations: Our power estimates were derived from prior data assessing sleep efficiency and nighttime BP dipping among individuals with HTN using the following assumptions: an initial sample size of 150 individuals, attrition of 15%, an alpha of 0.05, and a correlation of  $r = 0.30$  between sleep efficiency and BP dipping. Using these assumptions, we will have 80% power to detect correlations of  $r \geq 0.25$  between improvements in sleep efficiency and BP outcomes, suggesting that we will have adequate power to test the proposed hypotheses. In a more conservative scenario for comparing the worst 1/3 of the sample in terms of sleep efficiency change to the best 1/3, and assuming 50 participants in each group, there is 0.85 power at the two-sided 0.05 significance level for the detectable effect size  $\theta = 0.6$  via the following equation:  $(n \text{ per group}) = 50 = 2 * (((1.96 + 1.04) / 0.6) ** 2)$ . In the present proposal, this corresponds to a difference of 2.2% in SBP dipping between high and low sleep efficiency groups.

Exploratory Analyses of Effect Modification: In addition to our formal analyses, we will conduct exploratory analyses of effect modification, which will be interpreted as hypothesis generating. Candidate markers for effect modification will include background and clinical characteristics, such as race, gender, baseline insomnia severity, baseline anxiety, and the presence of elevated depressive symptoms ( $BDI > 14$ ). Specifically, we will examine the interaction terms between these candidate moderators, changes in sleep efficiency and mechanisms of CVD risk using the same general linear modeling approach noted for Hypothesis 2.

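### The 0.85 power for the extreme-thirds comparison leaves out the plan's own 15% attrition; with attrition it is about 0.79

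*Combined protocol and SAP*

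**What the plan says.** Power and Sample Size Considerations (Analysis Plan) gives two power figures.

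- The first lists its assumptions as "an initial sample size of 150 individuals, attrition of 15%, an alpha of 0.05" and a correlation of 0.30 between sleep efficiency and dipping. It then claims 80% power for correlations of at least 0.25 between improvement in sleep efficiency and blood pressure outcomes.
- The second is presented as a more conservative scenario, "comparing the worst 1/3 of the sample in terms of sleep efficiency change to the best 1/3". Its basis and conclusion come in one statement, "assuming 50 participants in each group, there is 0.85 power at the two-sided 0.05 significance level", for a standardised difference of 0.6. The plan prints the formula and equates 0.6 with 2.2% in systolic dipping.

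General Analytic Approach (Analysis Plan) also says that "we will exclude participants who no longer meet inclusion criteria following the 6-wk run-in period". The power paragraph does not mention this step, and no exclusion rate is given anywhere.

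The analysis plan for Aim 1 specifies general linear models of post-treatment dipping on improvement in sleep quality, with sleep efficiency named elsewhere as the primary, continuous index. No section plans a test between thirds.

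**The concern.** The two figures sit in one paragraph but rest on different numbers of participants. The first allows for the 15% loss. The second uses the whole enrolled sample, and it is the one labelled more conservative. A reader would take both as describing the same trial and could quote 0.85 power for a 2.2% difference, which the plan's own assumptions do not deliver.

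A second gap concerns the starting number. The plan does not say whether the 150, or the 15%, is counted before or after participants are removed at the end of the run-in. This matters because the first figure has little slack.

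**Working it through.** **Inputs, all from Power and Sample Size Considerations:** 150 initial participants; 15% attrition; two-sided alpha 0.05; standardised difference 0.6; z values 1.96 and 1.04; 2.2% dipping equated with 0.6, which implies an SD of 2.2/0.6 = 3.67 percentage points.

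**1. Reproduce the plan's figure.** n per group = 2 × ((1.96 + 1.04)/0.6)² = 2 × 25 = 50. Power = Φ(0.6 × √(50/2) − 1.96) = Φ(1.04) = 0.851, or 0.844 by noncentral t. The printed arithmetic is right, but 3 × 50 = 150, so it contains no attrition.

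**2. Confirm that the other figure does include attrition.** By the Fisher z approximation, power = Φ(atanh(0.25) × √(N − 3) − 1.96), with atanh(0.25) = 0.2554.

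- N = 127: 0.812
- N = 150: 0.872

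The stated 80% therefore fits the sample after attrition, not the full 150.

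**3. Apply the same attrition to the thirds.** 150 × 0.85 = 127.5, and 127.5/3 = 42.5 per third.

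| n per third | Plan's formula, Φ(0.6 × √(n/2) − 1.96) | t test |
|---|---|---|
| 50 | 0.851 | 0.844 |
| 43 | 0.794 | 0.785 |
| 42.5 | 0.790 | 0.780 |
| 42 | 0.785 | 0.776 |

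**4. Difference that does have 0.85 power.** (1.96 + 1.036) × √(2/42.5) = 0.650. On the plan's scale, 0.650 × 2.2/0.6 = 2.38, or about 2.4% (2.37% at 43 per third, 2.40% at 42).

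**5. Difference detectable at 80% power.** At 43 and 42 per third it is 0.604 and 0.611. Multiplied by 2.2/0.6, these are 2.21% and 2.24%. The 2.2% difference therefore stays detectable at roughly 79 to 80% power.

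**6. Slack in the correlation figure.** N for 80% power at r = 0.25 is (2.8016/0.2554)² + 3 = 123.3, so 124, against about 127 expected.

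**7. Run-in losses, for scale only.** The documents give no rate. If 5%, 10% or 20% were lost at run-in in addition to the 15% (an assumption), N would be 121, 115 or 102. Power for r = 0.25 would be 0.79, 0.77 or 0.72, and thirds power at 0.6 would be 0.77, 0.75 or 0.70.

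**The case against.** The strongest reply is that the thirds figure drives nothing. The planned analysis is a regression on sleep-efficiency change, the power claim that corresponds to it already allows for attrition, and the fifty per group is an openly displayed assumption with correct arithmetic. The label more conservative most naturally refers to discarding the middle third, not to attrition. All of this stands and limits the point to a minor one. It does not make 0.85 consistent with the loss assumed at the start of the paragraph. The planned multiple imputation does not rescue it either, since imputing missing outcomes does not restore the information they would have carried.

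Four stronger readings are tempting, and the documents do not support them.

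- *The trial is underpowered for its main question.* At N = 127 the power for r = 0.25 is 0.812. If the plan's assumed r = 0.30 applied to changes, which the plan does not state, power would be 0.93.
- *The 2.2% difference is out of reach.* It remains detectable at about 79 to 80% power; only the 0.85 attached to it is wrong.
- *The 80% claim collapses once four more participants are lost.* At N = 123 the power is 0.799. Power declines gradually, and 124 is only where it crosses 80%.
- *Run-in exclusions certainly reduce the analysed number further.* Purpose of the Study and Design & Procedures have all 150 receiving CBT-I, which follows the run-in, so 150 may already be net of those exclusions. The undefined 15% may also cover them. Against that, Safety Monitoring places completion of CBT-I about three months after enrolment, which matches six weeks of run-in plus six of treatment and suggests that enrolment comes first. The text does not settle it.

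**Conclusion.** The point holds as a minor correction. Under the plan's own 15% attrition, the extreme-thirds comparison has power of about 0.79 by the plan's normal formula (0.78 by t test) at a standardised difference of 0.6, not 0.85. Power of 0.85 corresponds to about 0.65, or about 2.4% dipping. This assumes that attrition falls evenly across the thirds and takes the plan's 2.2/0.6 conversion as given.

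The 80% claim for r ≥ 0.25 holds under the stated attrition. The run-in question supports only a request to define the numbers: its effect cannot be quantified from the documents, though a margin of 127 expected against 124 needed makes the definition worth stating.

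**What to change.** Replace the thirds sentence with wording such as:

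> With 15% attrition (about 42 per third), power is about 0.79 for a standardised difference of 0.6 (2.2% dipping); 0.85 power corresponds to about 0.65 (2.4% dipping). This comparison is illustrative; the planned analysis is a regression on change in sleep efficiency.

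In the same edit, state whether the 150 and the 15% are counted before or after the run-in exclusions, show the chain from enrolled to analysed, and note that 80% power for r = 0.25 needs about 124 analysed.

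The cost is wording only. One illustrative figure becomes slightly less favourable; enrolment, endpoints and planned tests do not change.

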#### C.6. QUALITY OF LIFE (QOL) ASSESSMENTS

CBT-I has been shown to result in marked improvements in QoL in medical patient populations where insomnia is commonly comorbid. In the present proposal, we will explore QoL changes that may accompany improved sleep quality following the CBT-I intervention. We will also explore QoL and psychosocial distress as potential moderators of the changes in CVD risk mechanisms accompanying sleep quality changes. A demographic information will be complete once and will be used to assess ethnicity, smoking, and alcohol use and menopausal status where applicable. The following assessments will be made at baseline, post-6-week run-in, post-CBT-I intervention, and at 6-month follow-up.

Health-Related Quality of Life will be measured using the Short Form-36 Health Survey (SF-36), which provides a physical health and mental health QoL summary score.

**Depressive Symptoms.** The Beck Depression Inventory II (BDI-II) will be used to assess depressive symptoms. It is a widely used self-report measure of depressive symptoms, consisting of 21 items, each corresponding to a specific category of symptoms and attitudes. The inventory has been studied extensively since it was first developed in 1961. It has been shown to be both a reliable and valid measure of the severity of depressive symptoms. In cardiac populations, depressive symptoms assessed using the BDI and the revised BDI-II, as well as changes in BDI over time, have been related to clinical outcomes. It should be emphasized that the BDI-II is not a diagnostic instrument, but rather a method for determining the presence and severity of depressive symptoms.

**Anxiety Symptoms.** Anxiety will be measured using the state and trait anxiety versions of the State-Trait Anxiety Inventory (STAI). The STAI consists of two separate 20-item self-report inventories, one measuring state anxiety and the other trait anxiety. The STAI has been shown to be associated prospectively with increased CVD risk and all-cause mortality.

Perceived Stress will be measured by the Perceived Stress Scale (PSS). The PSS consists of 10 items that are evaluated on a 5-point Likert scale.

Daytime Sleepiness will be assessed by the Epworth Sleepiness Scale (ESS), an 8-item measure of perceived daytime sleepiness.

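### The one depression moderator specified is binary (BDI > 14); if moderation is roughly linear in the score, the cut discards about 35–65% of its information.

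*Combined protocol and SAP*

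**What the plan says.** The Analysis Plan, under Exploratory Analyses of Effect Modification, announces "exploratory analyses of effect modification, which will be interpreted as hypothesis generating". It introduces the moderators with "Candidate markers for effect modification will include background and clinical characteristics, such as" and then names "race, gender, baseline insomnia severity, baseline anxiety" and "and the presence of elevated depressive symptoms". Only the last carries a threshold, BDI > 14. The test is described as follows: "we will examine the interaction terms between these candidate moderators, changes in sleep efficiency and mechanisms of CVD risk", using the linear-model approach of Hypothesis 2. I read this as a moderator-by-sleep-efficiency-change term, with the risk mechanism as outcome.

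Section C.6 describes the BDI-II as "consisting of 21 items, each corresponding to a specific category of symptoms and attitudes". It adds: "It has been shown to be both a reliable and valid measure of the severity of depressive symptoms". On timing it says: "The following assessments will be made at baseline, post-6-week run-in, post-CBT-I intervention, and at 6-month follow-up". The same section states an interest in quality of life and psychosocial distress as moderators and gives no cut-off for them.

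Neither section explains the choice of 14, and neither names the continuous BDI-II score as a moderator.

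**The concern.** A cut at 14 treats a participant scoring 15 like one scoring 40, and treats 14 and 15 as different. If the association between sleep improvement and a risk mechanism changes gradually with depressive symptoms, the binary term sees only part of that gradient, and its interaction test loses power.

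The stated power figures concern the main association between sleep-efficiency change and BP outcomes. Interaction tests usually have less power than main associations, so a coding choice that weakens them further is worth avoiding when the full score will already be in the database. What is at stake is how much the study can learn about distress as a moderator. Its main result is not at stake.

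The plan treats its primary mechanism outcome differently. Section C.5 keeps SBP dipping continuous as a primary outcome and uses the 10% dipper cut for description and secondary analyses.

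**Working it through.** **Inputs from the documents.** Enrolment is 150, attrition 15% and alpha 0.05 (Power and Sample Size Considerations). The moderator is BDI > 14. Analysed sample: 150 × 0.85 = 127.5, taken as 127.

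**Inputs not in the documents.** The share p of participants above 14 and the shape of the BDI-II distribution are not given. I assume p from 10% to 50%, with normal and right-skewed scores. I also assume a moderator effect linear in the score.

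**The plan's own figures.** None is given for the moderator analysis. The nearest figures reproduce:
- Power for r = 0.25 by Fisher z: atanh(0.25) × √(127 − 3) − 1.96 = 0.2554 × 11.136 − 1.96 = 0.884, so power is 0.81 (stated: 80%).
- Tertile comparison: 2 × ((1.96 + 1.04)/0.6)² = 50 per group, power 0.851 (stated: 0.85).

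**Information lost, normal score.** The share kept is φ(z)²/[p(1 − p)], where z is the normal quantile with share p above it.
- p = 0.50: 0.3989²/0.25 = 0.637 kept.
- p = 0.30: 0.3477²/0.21 = 0.576 kept.
- p = 0.20: 0.2800²/0.16 = 0.490 kept.
- p = 0.10: 0.1755²/0.09 = 0.342 kept.

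The equivalent sample is 127 × share kept. If the continuous term has 80% power, the binary term has power Φ((1.960 + 0.842) × √(share kept) − 1.960). For p = 0.30 this is Φ(2.802 × 0.759 − 1.960) = 0.57.

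**Information lost, right-skewed score.** For gamma scores the loss is 1 − corr(score, indicator)², with shape 1 the most skewed.

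| Share above 14 (assumed) | Loss, normal | Equivalent n of 127, normal | Power if continuous has 0.80, normal | Loss, gamma shape 1 | Loss, gamma shape 2 | Loss, gamma shape 4 |
|---|---|---|---|---|---|---|
| 50% | 36.3% | 81 | 0.61 | 51.9% | 44.7% | 40.6% |
| 40% | 37.8% | 79 | 0.60 | 44.0% | 38.9% | 36.9% |
| 30% | 42.4% | 73 | 0.57 | 37.9% | 35.9% | 36.1% |
| 25% | 46.1% | 68 | 0.54 | 35.9% | 35.7% | 37.3% |
| 20% | 51.0% | 62 | 0.50 | 35.2% | 37.0% | 39.8% |
| 15% | 57.4% | 54 | 0.45 | 36.5% | 40.3% | 44.3% |
| 10% | 65.8% | 43 | 0.37 | 41.0% | 46.8% | 51.8% |

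The extremes are 35.2% (gamma shape 1, 20% above) and 65.8% (normal, 10% above), hence about 35–65%.

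**Check on the interaction itself.** I simulated the regression with sleep-efficiency change, moderator and their product at n = 127 (4,000 runs per setting; independent standard normal score and sleep change; slope and interaction coefficients 0.25; residual SD 1).

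| Share above cut | Power, continuous | Power, binary | Loss |
|---|---|---|---|
| 50% | 0.76 | 0.56 | 36% |
| 30% | 0.75 | 0.52 | 44% |
| 20% | 0.76 | 0.45 | 53% |
| 15% | 0.77 | 0.40 | 60% |

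The simulated losses agree closely with the formula.

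**The case against.** Several points on the other side are sound.

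- A reader might infer that depression will be examined only as a two-level variable. The documents do not say so. The moderator list is open-ended, and section C.6 plans distress as a moderator with no cut-off. The plan is silent on a continuous BDI-II term and does not exclude one.
- A reader might infer an inconsistency, with insomnia severity and anxiety kept as continuous scores while depression is cut. The plan names those two as constructs and states no coding for them, and section C.4 itself reports a cut-off of 11 for the Insomnia Severity Index. The contrast cannot be shown.
- A reader might attach one narrower percentage to the loss. A range of 40–55%, for example, needs a normal score and 17–34% of participants above 14. Participants are not selected on depressive symptoms and the scale is bounded at zero, so right skew is plausible. With skewed scores and 20–30% above the cut, the loss is about 35–40%.
- If moderation really has a threshold near 14, the loss formula does not apply and the binary term may do well. Elevated symptoms can also be read as a deliberate clinical contrast.
- A reader might conclude that a null from the binary term would mislead. The plan draws no confirmatory inference here, and a null on the continuous term at n of about 127 could be weak evidence too.

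These points limit the size and consequence of the concern. They do not remove it: the only form of the depression moderator written down is the less efficient one for a graded effect, and no reason is given for it.

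**Conclusion.** The point holds as a modest improvement. For an effect roughly linear in the score, the specified cut costs at least about a third of the moderator's information in every scenario tried, and about 35–65% across them. The direction does not depend on the assumed share above 14 or on the skew, but the exact size does, and the documents fix neither.

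The consequence is confined to an exploratory analysis. The primary aim, the secondary hypotheses, the sample size and the stated power figures are unaffected.

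**What to change.** Under Exploratory Analyses of Effect Modification, name BDI-II at baseline (the post run-in assessment, which the General Analytic Approach already uses as baseline) as a continuous, centred moderator in the interaction model. Add a nonlinear term if a threshold shape is suspected. Keep BDI > 14 for describing the sample and for displaying fitted slopes.

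This is a free improvement. It changes only the coding of an exploratory model, needs no new data, visits or participants, and keeps the clinical contrast visible. The added nonlinear term would use a degree of freedom or more, so whether to include it should be settled before the outcome data are analysed.

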## D.2. METHODOLOGICAL ISSUES

For this mechanistic study, we considered several alternative designs, including a cross-sectional observational study and a two-group randomized design. A cross-sectional design was rejected because differences in CVD risk factors between patients with poor sleep quality and good sleep quality could be due to other factors besides their sleep. However, because the study objective was mechanistic, with the (favorable) manipulation of sleep quality of primary interest as the independent variable, and

because CBT-I has emerged as the gold standard for treating insomnia, we could not uphold the principle of equipoise in a design that randomized participants to an intervention that would likely be markedly less effective in treating their insomnia (e.g., sleep hygiene, no treatment, wait-list control). Moreover, the study objective is not to ascertain the efficacy of CBT-I, so a randomized design and comparison group is not required. Indeed, with the efficacy of CBT-I at approximately 60%, the more ethically defensible design was considered to be that all participants should receive the CBT-I intervention, with a time-equivalent run-in phase serving as a within-participant control phase to help establish that more marked alterations in sleep quality (60%) should be attributed to the CBT-I intervention, with an estimated 40% showing minimal to clinically insignificant changes.

A second aspect of our methodologic considerations was the selection of a primary measurement to serve as a manipulation check for sleep quality changes associated with the CBT-I intervention. We selected sleep efficiency, determined from actigraphy, because it is an objective and continuous measurement of sleep quality that: (i) has been shown to improve markedly following CBT-I; (ii) has been shown to be related to the development of hypertension, and; (iii) from our pilot studies, it is the index of sleep quality that was most clearly related to nighttime BP dipping and vascular endothelial function. Therefore, while sleep efficiency will serve as the primary index of sleep quality changes, we will also explore effects on other actigraphy-based sleep parameters, including total sleep time (TST), wake after sleep onset (WASO), and sleep fragmentation index (SFI). Insomnia aside, the evidence showing that poor sleep quality is a CVD risk factor has been based on large-scale meta-analytic studies of subjective measures of sleep quality and duration; this is because such data are widespread, and studies incorporating objective measures are relatively few. However, the available evidence shows that in smaller scale studies, objective measures of sleep quality show more robust associations with CVD risk. Nonetheless, we have included two important subjective measures of sleep, the ISI110 and the widely used PSQI, which we will use to provide supportive evidence of sleep quality changes and their association with changes in putative mechanisms relating sleep to CVD risk.

With respect to participant inclusion/exclusion criteria, we chose to focus on hypertension with comorbid insomnia because of the putative mechanisms of CVD risk, including blunted nighttime BP dipping, heightened sympathetic activity, arterial stiffness, and endothelial dysfunction being evident in this population, and therefore affording the opportunity for their improvement following CBT-I as a manifestation of sleep-related mechanisms of CVD risk. We also adopted the new ACC/AHA guidelines for defining hypertension at lower BP levels, with our selection of systolic BP  $\geq 130$  mm Hg as the inclusion criterion. We also excluded antihypertensive medication use, as different classes of medications have different half-lives and may distort the patient's normal circadian BP profile. Many individuals with recently diagnosed hypertension refuse antihypertensive therapy in favor of attempting lifestyle changes first; for those with comorbid insomnia, enrolling in our proposed study will provide them an opportunity to help control their BP, as well as improve their sleep. We also elected to exclude sleep apnea because of its association with hypertension presenting a potential confounding of our observations. Interestingly, a recent review and meta-analysis failed to find conclusive evidence that continuous positive airway pressure (CPAP) reduced the risk of CVD events in sleep apnea patients. However, in addition to compliance with CPAP therapy being difficult to ascertain, sleep apnea is frequently comorbid with insomnia, and when sleep apnea is diagnosed, comorbid insomnia is rarely treated, further complicating our understanding of sleep apnea and its treatment effect on BP.

